8.2 Safety and Efficacy Data Handling

8.2.1 Partial dates

Partial dates for AE and prior/concomitant medication, laboratory values, vital signs, and ECGs will not be imputed.

8.2.1.1 Diagnosis date

- If only the day of the month is missing, the 15th of the month will be used to replace the missing day
- If both the day and the month are missing, "July 1" will be used to replace the missing information

8.2.1.2 Date of Death

- If only the day of the month is missing, the 1st of the month will be used to replace the missing day

- If both the day and the month are missing, "Jan 1" will be used to replace the missing information
- If the entire date is missing, the date of death will be imputed as the last known date the subject was known to be alive + 1 day

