8.2.1.3 Date of Progression

- If only the day of the month is missing, the 1st of the month will be used to replace the missing day
- If the day and month are missing or a date is completely missing, it will be considered as missing and no date will be imputed

In case the date of death is present (complete date), the imputed progression date will be compared with the date of death. The earlier date of imputed progression date and date of death will be considered as the date of progression.

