8.3.4 Last Known Alive Date

The last date the subject was known to be alive should be derived from survival follow-up date or the latest date among last treatment date, last radiologic follow-up date, last laboratory assessment date, last AE date, last concomitant medication date, or last vital sign measurement date.

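### Partial death dates are imputed to 1 January or the 1st of the month without a last-known-alive floor, which can make duration of response (DOR) negative or too short

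*SAP*

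**What the plan says.** SAP 8.2.1.2 has three tiers for an incomplete date of death:

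- Day missing: "the 1st of the month will be used to replace the missing day".
- Day and month missing: "If both the day and the month are missing, 'Jan 1' will be used to replace the missing information".
- Everything missing: "the date of death will be imputed as the last known date the subject was known to be alive + 1 day".

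Only the third tier refers to the subject's other data. The variable it needs is defined in SAP 8.3.4: "The last date the subject was known to be alive should be derived from survival follow-up date", or otherwise from the latest of several other dates such as last treatment, scan, laboratory test or adverse event.

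For progression, SAP 8.2.1.3 also uses the 1st of the month when the day is missing. It does not go further: "If the day and month are missing or a date is completely missing, it will be considered as missing and no date will be imputed". Where a complete death date exists, it sets a ceiling: "The earlier date of imputed progression date and date of death will be considered as the date of progression". It sets no lower limit.

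Death is a DOR event in Table 3 of SAP 5.4.2.2, and the text below that table uses the earliest date when a subject has more than one event.

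**The concern.** The rules run backwards in information. A subject whose year of death is recorded can be dated as dying before a visit they attended. A subject with no death date at all cannot be, because that tier starts from last known alive.

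Other parts of the same section do bound their imputations. SAP 8.2.1.5 does not let an imputed start of new therapy fall on or before the last dose, SAP 8.2.1.6 caps an imputed radiotherapy stop at treatment start, and 8.2.1.3 caps progression at death. The missing floor for death looks like an oversight.

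At stake is DOR. A death dated before response gives a negative duration, and the SAP has no rule for handling one. A death dated before the last contact shortens DOR against recorded data.

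**Working it through.** The plan states no figure on this point, so there is none to reproduce. The check applies the written rules to dated examples.

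**Inputs.** Phase 2 scans at Weeks 8, 16 and 24 (SAP 3.2.2 and 3.2.3); confirmation at least 4 weeks after first response (SAP 5.4.1.2); DOR from first documented confirmed response to progression or death (SAP 5.4.2.2). Formula: DOR = event date - first response date + 1. The + 1 is an assumption; the SAP does not state it.

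**Example 1, only the year of death known.** First dose 10 March 2021; PR at Week 8, 5 May; confirmed at Week 16, 30 June; last known alive 1 October; true death 20 October.

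- True DOR: 5 May to 20 October is 168 days, + 1 = 169.
- SAP rule: death on 1 January 2021. That is 68 days before first dose, 124 before response and 273 before last known alive. DOR = -124 + 1 = -123.
- With a floor at last known alive + 1 day (2 October): DOR = 150 + 1 = 151.

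**Example 2, same subject, only the day missing, last known alive 14 October.**

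- SAP rule: death on 1 October, 13 days before last known alive. DOR = 149 + 1 = 150.
- With the floor (15 October): 163 + 1 = 164. True value 169.

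**Example 3, documented progression displaced.** Take Example 1 and add PD at the Week 24 scan, 25 August. The correct DOR is 112 + 1 = 113. Under the SAP rule the earliest event is the imputed death of 1 January, so DOR is again -123. With the floor, death falls on 2 October, progression comes first, and DOR is 113.

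**Example 4, event status changed.** Table 3, situation 6, censors a death in the Extension Phase that falls more than 181 days after the last adequate scan. Last scan 15 September 2021, last known alive 1 April 2022, true death 20 June 2022, only the year known.

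| Death date used | Days after last scan | Outcome |
|---|---|---|
| True, 20 June 2022 | 278 | Censored |
| SAP rule, 1 January 2022 | 108 | Event |
| Floor, 2 April 2022 | 199 | Censored |

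**How often each rule gives an impossible order.** A confirmed responder dies at least 28 days after first response.

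- Day-missing rule: over 543,120 combinations of response date (four calendar years) and death 28 to 399 days later, imputed death preceded response in 72 + 28 = 100. In all of them response was on the 2nd or 3rd of a month and death at the end of that month; the error was 1 or 2 days.
- 1 January rule: death precedes response whenever both fall in the same calendar year and response is after 1 January. The lowest DOR found was -335 days.

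**Largest shift.** Day missing: 31st to 1st, 30 days. Day and month missing: 31 December to 1 January, 364 days in a non-leap year.

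**Progression, day missing.** Last scan without progression 12 August, true progression 30 August: imputed 1 August, 11 days before a scan that showed none.

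**The case against.** Four arguments weigh against the point.

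1. SAP 5.3 calls the imputation conservative, describes 8.2.1 as an outline and leaves detail to dataset specifications that are not among the documents. Those could contain a floor. So it cannot be said that the analysis will produce impossible dates. It can be said that the SAP's rule, followed as written, produces them, and that nothing in it requires a floor. Early dating is conservative for DOR only while it stays consistent with recorded data.
2. A reader might infer that both partial-date rules commonly give an impossible DOR. The 4-week confirmation rule prevents that: the day-missing rule reverses the order only in the narrow case shown above. A day-missing death can also be dated before first dose, but that subject has no confirmed response and so no DOR.
3. The trigger looks rare. Survival is followed every 3 months for a year (SAP 3.2.6.1), and serious adverse events go to the sponsor within one business day (24 hours at EU sites), with supporting reports (Protocol 9.5.4.1). Progression dates are scan dates, and 8.2.1.3 imputes nothing when the month is missing, so that part is minor. This stands.
4. A floor with no upper limit could override a recorded month or year of death if some other date in 8.3.4 falls later. This also stands, and the fix allows for it.

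**Conclusion.** SAP 8.2.1.2 is wrong as written, at low severity. The 1 January rule can put death before response or first dose and make DOR negative. The day-missing rule mainly shortens DOR, by up to 30 days, and can contradict a documented living contact. Either error can displace a later documented progression or change event or censoring status.

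The effect stops at DOR and outputs that use the death date. A reader might infer that the efficacy conclusion is exposed, but ORR at Week 16 and the futility rule do not use death dates, and the SAP's endpoints include neither PFS nor OS.

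A reader might also infer that one bad date must move the median DOR. It can, but need not. A full cohort at the alternative rate gives 0.25 x 20 = 5 responders. If none is censored, the median is the third value. Moving a subject from the third place or above to the bottom changes it; moving one of the two shortest does not.

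The documents give no count of partial death dates. The conclusion rests on the SAP text alone, without the dataset specifications.

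**What to change.** In SAP 8.2.1.2, for the two partial-date tiers, set the imputed death date to the later of the present rule date and last known alive + 1 day. Keep the result within the recorded month (day missing) or recorded year (day and month missing). Count only contacts at which the subject was alive. If last known alive falls after the recorded period, raise a data query and do not impute over the conflict.

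As a minor parallel change in SAP 8.2.1.3, let an imputed progression date be no earlier than the day after the last adequate assessment without progression, within the recorded month.

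The cost is a few lines in the SAP and the dataset specification. The last known alive variable is already defined, and no new data are needed.

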8.2.1.3 Date of Progression

- If only the day of the month is missing, the 1st of the month will be used to replace the missing day
- If the day and month are missing or a date is completely missing, it will be considered as missing and no date will be imputed

In case the date of death is present (complete date), the imputed progression date will be compared with the date of death. The earlier date of imputed progression date and date of death will be considered as the date of progression.

8.2.1.4 Date of Last Tumor Assessment

- If only the day of the month is missing, the 1st of the month will be used to replace the missing day
- If the day and month are missing or a date is completely missing, it will be considered as missing and no date will be imputed

In case the date of death is present (complete date), the imputed date for tumor assessment parameters will be compared with the date of death. The earlier date of the imputed date and date of death will be considered as the date of last tumor assessment.

8.2.1.5 Date of Start of Subsequent Anticancer Therapy

- When the day is missing, it is assumed that the subsequent therapy started on the first day of the given month if this day is later than the last date of drug administration. Otherwise, it is assumed that the subsequent therapy started on the day following the last date of drug administration.
- When the day and the month are missing, it is assumed that the subsequent therapy started on the first day of the given year if this day is later than the last date of drug administration. Otherwise, it is assumed that the subsequent therapy started on the day following the last date of drug administration.

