5.3 Data Analysis General Considerations

For incomplete dates involving efficacy and other safety data, a conservative imputation will be used for calculation. See [Section 8.2.1](#) for the outline of imputation rules, which will be specified in the study analysis dataset specifications with more details.

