- DOR: defined as the time from the date of first documented confirmed CR or PR to disease progression objectively documented or death (whichever comes first). The DOR will be analyzed using the Kaplan-Meier (KM) ([Kaplan and Meier, 1958](#)) method among the responders (CR or PR). The DOR will be analyzed using the KM approach among the responders (CR or PR) according to the rules in [Table 3](#).

5.4.2.2 Phase 2

Subjects must have measurable disease at baseline for enrollment in Phase 2. The secondary efficacy endpoints ORR at the time of data cutoff, DCR, CBR and DOR will be performed for subjects in the Evaluable Analysis Set.

- ORR at the time of data cutoff: defined as the proportion of subjects achieving a best overall response of confirmed PR or CR at the time of data cutoff. ORR and corresponding exact 95% CI using the Clopper-Pearson method will be estimated for all Phase 2 treatment disease cohorts.
- DCR: defined as the proportion of subjects who have a BOR of CR or PR or stable disease (SD). To be assigned a best overall response of SD, the time from the first dose of study treatment until the date of documented SD should be ≥ 7 weeks. The count and percentage with exact Clopper-Pearson 95% CI for the DCR will be summarized for all Phase 2 treatment disease cohorts.
- CBR: defined as the proportion of subjects with who have a BOR of CR or PR or durable SD lasting ≥ 23 weeks. The count and percentage with exact Clopper-Pearson 95% CI for the CBR will be summarized for each Phase 2 treatment disease cohort.

- DOR: defined as the time from the date of first documented confirmed CR or PR to disease progression objectively documented or death (whichever comes first). The DOR will be analyzed using the Kaplan-Meier (KM) ([Kaplan and Meier, 1958](#)) method among the responders (CR or PR) according to the rules in [Table 3](#).

• Table 3 DOR and Censoring Rules			
No.	Situation	Date of Progression or Censoring	Outcome
1	Progression documented between scheduled visits, on or prior to new anticancer therapy	Date of first radiologic PD assessment	PFS Event
2	No progression at the time of data cutoff	Date of last adequate radiologic assessment on or prior to data cutoff	Censored
3	New anticancer therapy started before the first PD or death	Date of last adequate radiologic assessment on or prior to the start of new anticancer therapy	Censored
4	Death before first PD assessment, on or prior to start of new anticancer therapy	Date of death	PFS Event

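### The rule for partial new-therapy dates is not checked against documented progression, so some DOR events can be lost to censoring

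*SAP*

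**What the plan says.** SAP 8.2.1.5 places a partial start date of subsequent anticancer therapy as early as the recorded part allows. With the day missing, "the subsequent therapy started on the first day of the given month"; with day and month missing, "the subsequent therapy started on the first day of the given year". Either date is used only "if this day is later than the last date of drug administration". If it is not, the start becomes the day after the last dose. No other date is compared.

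Table 3 in SAP 5.4.2.2, which also governs DOR in Phase 1, uses the therapy start to decide between event and censoring. Row 1 counts as an event "Progression documented between scheduled visits, on or prior to new anticancer therapy". Row 3 applies when "New anticancer therapy started before the first PD or death" and censors at the last adequate scan on or before that start. The priority notes below the table make no exception for a therapy date that was imputed.

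SAP 5.3 says that for incomplete dates "a conservative imputation will be used for calculation". It calls 8.2.1 an outline and leaves further detail to the dataset specifications.

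**The concern.** The imputed start decides whether a scan-documented progression counts. If therapy followed PD but its date is known only to the month or year, placing the start at the earliest possible day can reverse the order of the two dates. Row 3 then replaces an observed event with a censored time at an earlier scan.

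The route exists under this protocol. Subjects who stop drug for reasons other than progression are followed for PD for up to 1 year or until new therapy (SAP 3.2.6.1), with scans every 12 weeks (protocol 9.5.1.3.1). PD well after the last dose is therefore expected in some subjects.

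The neighbouring rules do cross-check. SAP 8.2.1.3 and 8.2.1.4 compare with the date of death, and 8.2.1.6 compares with the start of treatment. 8.2.1.5 lacks a check against the date that settles event status. Losing true events usually lengthens the estimated DOR, which fits poorly with an imputation described as conservative.

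**Working it through.** **Rule as a formula.** Let L be the last dose, F the first day compatible with the recorded date (1st of the month, or 1 January), P the documented PD date and N the imputed start.

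- SAP 8.2.1.5: N = F if F is later than L, otherwise L + 1. This is N = max(F, L + 1).
- Table 3 rows 1 and 3: event at P if P ≤ N. If N < P, censored at the last adequate scan on or before N.
- So, when therapy truly followed PD, the event is lost exactly when P is later than F and L is at least 2 days before P.

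**Dated cases, PD on 15 June:**

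| Last dose | True start | Recorded as | Imputed start | Result |
|---|---|---|---|---|
| 20 May | 25 June | June | 1 June | censored |
| 20 May | 25 June | year only | 21 May | censored |
| 10 June | 25 June | June | 11 June | censored |
| 14 June | 25 June | June | 15 June | event kept |
| 15 June | 25 June | June | 16 June | event kept |
| 20 May | 5 July | July | 1 July | event kept |
| 20 May | 5 July | year only | 21 May | censored |

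The correct outcome in every row is an event on 15 June. If the previous adequate scan was 12 weeks before PD (23 March), each censored row loses the event and 84 days.

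**Share of PD dates exposed.** Assume L ≤ P − 2, a partial therapy date, therapy k days after PD, and PD equally likely on each day of a 365-day year. With the day missing, a month of D days loses PD dates from the 2nd to day D − k, which is D − k − 1 dates. Summed over 12 months this is 365 − 12(k + 1); at k = 28 February contributes 0 instead of −1. With only the year known it is 365 − k − 1.

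| k (days) | Day missing | Year only |
|---|---|---|
| 7 | 269/365 = 74% | 357/365 = 98% |
| 14 | 185/365 = 51% | 350/365 = 96% |
| 21 | 101/365 = 28% | 343/365 = 94% |
| 28 | 18/365 = 5% | 336/365 = 92% |

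If the last dose was 0 or 1 day before PD, the share is 0%.

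**Number of responders.** The exact two-stage calculation (stop at 0 of 10, failure at 2 or fewer of 20) gives power 0.882 at 25% and type I error 0.0686 at 5%, matching the plan's 88% and 0.07. Expected responders in 20 are 20 × 0.25 = 5 at the alternative and 20 × 0.05 = 1 at the null; 3 is the fewest that avoids failure.

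**Effect on the median.** Assume five responders, all with events, at 56, 112, 196, 280 and 364 days. Survival falls to 0.8, 0.6 and then 0.4 at 196, so the median is 196 days.

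- Third responder censored 84 days earlier, at 112: survival is 0.8 at 56, 0.8 × 3/4 = 0.6 at 112 and 0.6 × 1/2 = 0.3 at 280. The median becomes 280 days.
- Fourth responder censored 84 days earlier, at 196: survival at 196 is 0.6 × 2/3 = 0.4. The median stays at 196.
- Fifth responder censored 84 days earlier, at 280: nothing changes up to 196. The median stays at 196.

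**The case against.** **The exposed group is narrow.** Treatment is meant to continue until progression, so many responders will still be on drug at PD and the floor keeps their events. A lost event needs a confirmed responder who stopped at least 2 days before PD, had PD documented later, and has a partial therapy date in the PD month or year. A reader might infer that PD and therapy in the same month always produce censoring; the floor shows that they do not. This stands and limits the size of the point.

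**Conservative is not defined.** An early therapy start avoids crediting response under another drug to the study treatment, which is a defensible aim. It does not justify discarding a documented PD when the recorded date cannot show that therapy came first.

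**The fix assumes the opposite order.** A subject may stop drug and start new therapy shortly before a PD scan in the same month, and would then count as an event. This is a real cost, but probably a small one: planned scans stop at PD or new therapy, so where a PD is documented and the therapy date is ambiguous, PD most plausibly came first.

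**The dataset specifications may contain the check.** They may; they are not among the documents. The SAP rule as written still gives the wrong result, and a rule that decides event status belongs in the SAP.

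**Death.** 8.2.1.5 makes no comparison with death either, and a reader might want the same lower bound there. The case differs: a recorded therapy cannot have started after death, so for a death without PD row 3 censoring is the intended outcome.

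**Conclusion.** The point holds within limits. SAP 8.2.1.5 and Table 3 together can turn a documented progression into a censored DOR when the last dose was at least 2 days before PD and the partial therapy date shares the PD month, or the PD year if only the year is known.

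Its weight is modest. DOR is secondary and descriptive. A reader might infer that the Phase 2 conclusions are at risk, but Week 16 ORR, the futility look and the failure rule do not use the therapy date. Nor does every such case move the median: in the illustration the third responder does, and the fourth and fifth do not. What can be said is that with about 5 responders one case can move it, usually towards longer DOR.

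The lags, the 12-week gap to the previous scan and the five durations are assumptions. How many subjects have partial dates, or stop drug before PD, cannot be read from the documents. The change is worth making because the rule is wrong for a foreseeable case and the correction is cheap.

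**What to change.** Add to SAP 8.2.1.5: when the recorded part of the date is compatible with a start on or after documented PD, the imputed start is the later of the date under the current rule and the PD date. Row 1 accepts PD on the day therapy starts, so all the dated cases above return to an event on 15 June. Row 3 then applies only when the recorded part of the date shows that therapy began before PD. For death, no lower bound is needed; it is enough to state that the imputed start may not be later than the date of death.

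List the subjects whose DOR status depends on an imputed therapy date, and report DOR under the current rule as a sensitivity analysis, so that the few who may have started therapy just before PD are visible.

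The cost is one SAP sentence, one line in the date derivation and one short listing with a repeat of the DOR table. Sample size, power and type I error do not change.

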8.2.1.6 Date of Previous Radiotherapy

- If only the start day of the month is missing, the 1st of the month will be used to replace the missing day

- If both the start day and month are missing, "Jan 1" will be used to replace the missing information
- If only the stop day of the month is missing, the latest possible day of the month will be used to replace the missing day
- If both the stop day and month are missing, "Dec 31" will be used to replace the missing information

In case the date of treatment start day is present (complete date), the imputed radiotherapy stop date will be compared with the date of treatment start day. The earlier date of imputed radiotherapy stop date and date of treatment start day will be considered as the stop date of radiotherapy.

8.3 Definitions, Derived Variables, and Data Sets

8.3.1 Baseline

Baseline value is defined as the predose value on Cycle 1 Day 1 or the last observation before start of drug if the predose value on Cycle 1 Day 1 is missing.

8.3.2 Date/Time Definitions

The following factors will be used to convert days to months:

1 month = 30.4375 days

- Time from first diagnosis to first dose (months) is:
 $(\text{Date of first dose} - \text{Date of first diagnosis}) / 30.4375$
- Time from first metastatic diagnosis to first dose (months) is:
 $(\text{Date of first dose} - \text{Date of first metastatic diagnosis}) / 30.4375$
- Time from last medication to first dose (months) is:
 $(\text{Date of first dose} - \text{End date of last medication}) / 30.4375$
- Time from last anthracycline therapy to first dose (months) is:
 $(\text{Date of first dose} - \text{Start date of the last anthracycline therapy}) / 30.4375$
- Time from last radiotherapy to first dose (months) is:
 $(\text{Date of first dose} - \text{End date of the last radiotherapy}) / 30.4375$

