5.2.4 Demographic and Other Baseline Characteristics

Demographic and baseline characteristics for the Safety Analysis Set will be summarized by dose level group and overall in Phase 1, and separately for each study cohort in Phase 2.

The following demographic and baseline characteristics will be summarized as appropriate:

- Age (years)
- Age group (2 to <6 years, 6 to <12 years, 12 to <16 years, 16 to <18 years, 18 to 21 years, if applicable)
- Gender
- Race

- Ethnicity
- Baseline Karnofsky/Lanksy performance status score
- Height (cm)
- Height Percentile
- Baseline weight (kg)
- Baseline body mass index (BMI) (kg/m²)
- Body Surface Area

Previous anticancer medication will be summarized by dose level group and overall in Phase 1, and separately for each study cohort in Phase 2 as follows:

- Number of previous therapy regimens
- Duration of most recent previous anticancer therapy (months)
- Best response for most recent previous anticancer therapy (CR, PR, SD, progressive disease (PD), not evaluable, not applicable, unknown)
- Time from end of most recent previous anticancer therapy to first dose of study drug (months)
- Previous anticancer therapy (administered as adjuvant, neoadjuvant, metastatic, locally advanced, maintenance and unknown)
- Previous anticancer therapy preferred term

Previous anthracycline therapy will be summarized by dose level in Phase 1 and by each cohort in Phase 2 as follows:

- Number of subjects with any previous anthracycline therapy
- Duration of most recent previous anthracycline therapy (months)
- Time from end of most recent previous anthracycline therapy to first dose of study drug
- Previous anthracycline therapy preferred term

Previous radiotherapy will be summarized by dose level in Phase 1 and by cohort in Phase 2 as follows:

- Subjects with any previous radiotherapy
- Radiotherapy site (lymph node [neck/thoracic/abdominal and pelvic/other], bone [skull/spine/thorax/pelvis/extremities], brain, visceral [colorectal mass, lung mass, liver mass, chest, abdomen/pelvis], skin [trunk, extremity, head and neck], musculoskeletal [soft tissue-trunk, extremity, head and neck], miscellaneous)
- Tumor lesion at the site progressed since most recent previous radiotherapy (yes, no, not evaluated)
- Time from most recent previous radiotherapy to the first dose.

- Duration of most recent previous radiotherapy

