9 PROGRAMMING SPECIFICATIONS

The rules for programming derivations and dataset specifications are provided in separate documents.

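### SAP 8.3.2 measures time since last anthracycline therapy from its start date, while SAP 5.2.4 plans the interval from its end

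*SAP*

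**What the plan says.** SAP 5.2.4 (Demographic and Other Baseline Characteristics) sets out a block of summaries on previous anthracycline therapy, by dose level in Phase 1 and by cohort in Phase 2. One row is "Time from end of most recent previous anthracycline therapy to first dose of study drug". The length of the most recent anthracycline therapy, in months, is a separate row in the same block.

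SAP 8.3.2 (Date/Time Definitions) gives the formulas. Under the label "Time from last anthracycline therapy to first dose (months) is", the date subtracted from the date of first dose is the "Start date of the last anthracycline therapy". The corresponding line for last medication uses "End date of last medication" and the line for last radiotherapy uses "End date of the last radiotherapy". All three divide by the same factor, "1 month = 30.4375 days".

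SAP 9 adds: "The rules for programming derivations and dataset specifications are provided in separate documents".

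**The concern.** The table definition and its derivation describe different quantities, and a programmer cannot satisfy both. The table asks how long a subject had been off anthracyclines at first dose. The formula returns how long ago the last anthracycline therapy began, so the treatment period itself is counted as time since treatment.

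The SAP's own text points to the formula as the slip. It is the only one of the three prior-treatment intervals in 8.3.2 that uses a start date. The duration of therapy already has its own row in 5.2.4, so with the start date the same span is counted again inside the interval row. For a subject whose most recent anticancer therapy was the anthracycline, the anticancer row and the anthracycline row should agree; as written, they would differ by the length of that therapy.

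At stake is the accuracy of one descriptive row. A reader of the published table could not repair it, because subtracting the median duration from the median interval does not in general give the median of the individual differences.

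**Working it through.** There is no stated figure to reproduce. The check is algebra on the 8.3.2 formula, with illustrative dates.

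**Inputs from the documents**
- Planned quantity: interval from end of therapy to first dose (SAP 5.2.4).
- Date subtracted in the derivation: start of therapy (SAP 8.3.2).
- Conversion: 30.4375 days per month (SAP 8.3.2).

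**Input not in the documents**
- Length of the last anthracycline therapy, L = end date − start date, in days. Values from 0 to 180 are assumed below.

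**Formulas**
- As written: A = (first dose − start)/30.4375
- As planned: B = (first dose − end)/30.4375
- Excess: A − B = (end − start)/30.4375 = L/30.4375

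The excess does not depend on the gap between the end of therapy and first dose. It is never negative, and it is zero only when therapy starts and ends on the same date.

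| Assumed L (days) | Excess (months) |
|---|---|
| 0 | 0.00 |
| 1 | 0.03 |
| 2 | 0.07 |
| 21 | 0.69 |
| 84 | 2.76 |
| 180 | 5.91 |

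**Worked example.** Suppose therapy lasted 84 days and ended 180 days before first dose.
- As written: (180 + 84)/30.4375 = 264/30.4375 = 8.67 months.
- As planned: 180/30.4375 = 5.91 months.
- Difference: 2.76 months, which equals 84/30.4375.

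Running the same lengths with gaps of 30, 180 and 365 days to first dose gave the same excess each time.

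**The case against.** Four points can be made on the other side.

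1. **The error may never reach the report.** Detailed derivation rules sit in separate specifications that are not available here, and these may follow 5.2.4. This stands: the overstatement is conditional on 8.3.2 being programmed as written. It does not remove the conflict inside the SAP.

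2. **Not every interval would be wrong.** A reader might infer that all reported values are too long. That goes too far, since a record that starts and ends on the same date carries no error. The size also depends on whether a therapy is recorded by single administration or by whole course, which the SAP and protocol do not say.

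3. **No cardiac analysis is distorted.** Because the SAP also plans summaries of LVEF and shortening fraction (5.6.4) and lists cardiac dysfunction among the clinically significant events (5.6.2), a reader might infer that those analyses lean on this interval. They do not. None is stratified by or related to time since anthracycline, SAP 5.3.2 rules out covariate adjustment, and SAP 5.3.4 leaves subgroup analyses optional without naming any. Someone might informally read cardiac findings against this row, but that is a use by the reader and not a planned analysis.

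4. **The mistake may be noticed.** SAP 5.2.4 also calls for a per-subject listing of anthracycline therapy and a separate duration row, so a check against them could expose it. This is partial mitigation only.

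**Conclusion.** The inconsistency is real, and its direction and size follow exactly from the formula. If 8.3.2 is followed as written, the interval for any course longer than one day is overstated by (end date − start date)/30.4375 months, and exposure looks older than it was.

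The range of 0 to 5.9 months is illustrative and rests on assumed lengths of 0 to 180 days. Protocol section 7 describes a doxorubicin-containing first-line regimen for Ewing sarcoma given at 2-3 week intervals, but gives no total duration, so the documents do not support a typical figure of several months.

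The consequence is minor. The Week 16 response rate, the two-stage futility rule and the planned safety analyses do not use this variable. Nor does eligibility: the chemotherapy washout in protocol 9.3.1 is counted in days after the last dose.

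**What to change.** In the anthracycline line of SAP 8.3.2, replace the start date with the end date, giving (date of first dose − end date of the last anthracycline therapy)/30.4375. This agrees with 5.2.4 and with the medication and radiotherapy formulas. Then confirm that the separate programming specification uses the end date.

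The cost is one word in the SAP and one check of the specification, with no effect on design or sample size. The planned duration row already needs both a start and an end date, so no new data should be required.
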